### 5.1.1.4 Drug reconciliation procedures

Accountability of the investigational study drug is under the responsibility of the investigator and can be delegated to an appropriately qualified person.

Study drug accountability should be maintained by each site. Accountability records should include receipt date, batch numbers, expiry dates, patient SeqID, use by subject, dispensing dates, quantities (lowest unit) and stock balance.

In addition to internal accountability documentation on site, EORTC study-specific accountability and drug destruction forms will be supplied for this purpose, if site-specific forms are deemed not sufficiently detailed or do not provide enough information, according to EORTC Quality Assurance criteria.

The drug accountability and destruction forms will be verified during monitoring visits.

At the end of study, when all patients have stopped protocol treatment, complete drug reconciliation per batch should be available at the site for verification by EORTC in order to allow drug destruction or return procedure.

Both the unused and expired study medication must be destroyed, upon authorization of the sponsor, according to local regulations and procedures, and a copy of the destruction form must be returned to the EORTC Headquarters.

The medication provided for this trial is to be used only as indicated in this protocol and only for the patients entered in this study.

## 5.1.2 Temozolomide

Temozolomide (TMZ) is an approved drug for the treatment of patients with newly diagnosed glioblastoma. TMZ is available commercially and will therefore be taken off the shelf.

During radiotherapy, TMZ is administered at a dose of 75 mg/m^2 daily, starting at the first day of radiotherapy, typically for 42 days and for a maximum of 49 days. Four weeks after the last day of radiotherapy, treatment with TMZ is resumed at a dose of 150 mg/m^2 (cycle 1) and 200 mg/m^2 (subsequent cycles) daily for 5 days every 28 days (corresponding to a cycle) for up to 6 cycles. TMZ will be administered and prescribed according to the official label and the standard of care which has been defined in a previous EORTC/NCIC trial (Ref. 42).

## 5.2 Initial dose and schedule

MRZ will be administered IV over 10 minutes. Volume of administration will vary based on dose (0.8 mg/m^2) and patient body surface area (BSA). Capping is not allowed, because of potential underdosing. MRZ can be administered either through peripheral, PIC-line, central line or port-a-cath at investigator discretion. However, infusion site reactions are observed with peripheral administration; infusing by central line reduces the frequency and severity of these events (refer to Pharmacy Manual).

Patients should maintain good oral hydration during the study (e.g., 2 L/day). The volume and duration of hydration may be reduced at the discretion of the Investigator, especially for patients with low body weight or with conditions sensitive to fluid overload.

Patients should not drive a vehicle or operate heavy machinery while on this study.

MRZ will be administered as a 10-minute IV infusion on Days 1, 8, 15, 29 and 36 during the concomitant treatment (with TMZ+RT), and on Days 1, 8, and 15 of each 28-day cycle in adjuvant treatment (with TMZ) for a total of 6 cycles. After 6 cycles of TMZ have been completed, marizomib is administered on Days 1, 8, and 15 of each 28-day cycle for another 12 cycles.

Minimum re-treatment criterion prior to the beginning of each new cycle in the adjuvant treatment: creatinine  $\leq$  1.5 x ULN, Hgb  $\geq$  8 g/dL, platelets  $\geq$  75 x 10^9/L.

## 5.3 Treatment duration

In the standard arm, patients will receive up to 6 cycles of TMZ as maintenance at a dose of 150-200 mg/m^2 daily for 5 days every 28 days, unless treatment is discontinued for disease progression, unacceptable toxicity, or withdrawal of consent.

Continuation of maintenance temozolomide beyond 6 cycles (e.g., for a maximum of 12 cycles) is not encouraged but is left to the discretion of the Investigator and the interest of the patient.

In the experimental arm, patients will receive up to 6 cycles of MRZ+TMZ in the maintenance setting, followed by another 12 cycles of MRZ alone, unless treatment is discontinued for disease progression, unacceptable toxicity, withdrawal of consent, or the patient has completed the 18 cycles of MRZ as planned. In the event that one drug (TMZ or MRZ) is discontinued for reasons other than disease progression, the other will then continue as a single agent.

At study closure, all study participants may continue to receive study treatment as planned in the protocol (see chapter 4) provided that they benefit from it and all protocol-specified criteria for continuing study treatment are met. For all patients who discontinue treatment for reasons other than disease progression, whenever possible, tumor assessment will continue as per protocol until disease progression, or start of a new treatment regimen.

After disease progression, treatment will be left to the discretion of the treating physician. Any further anti-cancer therapy will not be considered as part of the protocol treatment. However, patients will be followed for survival and the start of first new anti-GBM therapy and its outcome.

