|--|---|

|  |  |
|--|--|
|  | 
subject has completed potentially curative treatment more than 3 years prior to study entry are allowed.
 
 
• Presence of any psychological, familial, sociological or geographical condition potentially hampering compliance with the study protocol and follow-up schedule; those conditions should be discussed with the patient before registration in the trial.
 
   |
| 
Treatment
 
Test product, dose and mode of administration
 
Duration of treatment
 | 
Experimental arm: Standard radiotherapy ( RT)(60 Gy in 30 fractions over 6 weeks) + TMZ 75 mg/m^2 p.o. daily for 6 weeks (during radiotherapy) and marizomib (MRZ) dose 0.8 mg/m^2 IV at days 1, 8, 15, 29 and 36.
 
This is followed, after 4-week break, by up to 6 cycles of maintenance TMZ 150-200 mg/m^2 p.o. on days 1-5 of a 28-day cycle and up to 18 cycles of maintenance MRZ treatment (0.8 mg/m^2 IV) at days 1, 8, 15 of a 28-day cycle until disease progression, unacceptable toxicity or withdrawal of consent.
 
Standard arm: Standard radiotherapy (RT) (60 Gy in 30 fractions over 6 weeks) + TMZ 75 mg/m^2 p.o. daily for 6 weeks (during radiotherapy) then (after 4-week break) up to 6 cycles of maintenance TMZ 150-200 mg/m^2 p.o. on days 1-5 of a 28-day cycle.
 
All patients will have regular follow-up by MRI, 4 weeks after the end of radiotherapy (RT), then every 8 weeks thereafter until progression.
 
Once patients stop study treatment, they will be followed as per institution's standard.
 |

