### 6.3.2 Post Treatment Follow-up (every 12 weeks $\pm$ 7 days)

#### 6.3.2.1 Patient has not progressed

- results of MRI scans done as part of standard of care will be collected, or done as per the study schedule of every 8 weeks (continuing on initial schedule) until disease progression.
- MMSE, Quality of life assessment (modified EORTC QLQ C30/BN20) every 16 weeks  $\pm$  2 weeks
- For participating centers, tests of objective neurocognitive function: HVLT-R, Trail Making Tests Part A & B and COWA and the MOS questionnaire on self-perceived neurocognitive function (Appendix J) every 12 weeks ( $\pm$  7 days)
- survival status
- subsequent anti-GBM regimens, and treatment outcomes

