### **7.1.1.3 Schedule of disease evaluation**

The initial assessment of disease (including measurement of all target lesions) must be performed in the two weeks preceding randomization. Follow-up assessments will be performed every 8 weeks (or earlier if clinically indicated) until disease progression.

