## 7.1.3 Progression Free Survival

Progression Free Survival (PFS): PFS is defined as the number of days from date of randomization to the date of earliest disease progression based on Response Assessment in Neuro Oncology (RANO) criteria (as determined by the Investigator) or to the date of death due to any cause, if disease progression does not occur. Patients for whom neither death nor progression have been documented will be censored on the date of the last radiological assessment that the patient was progression-free. If a patient with no post-baseline radiological assessment then the data will be censored at the date of randomization. Patients with two or more missing response assessments prior to a visit with documented disease progression (or death) will be censored at the last visit where the patient was documented to be progression free. Patients who received new anti-cancer therapy or cancer-related surgery prior to progression or death will not be censored at the last assessment where the patient was documented as progression free prior to the new anti-cancer therapy or cancer-related surgery. Detailed censoring rules will be documented in the SAP.

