11.3.1. Progression-free Survival

Progression-free survival will be defined as the number of days from date of randomization to the date of earliest disease progression based on Response Assessment in Neuro-Oncology (RANO) criteria (as determined by the Investigator) or to the date of death due to any cause, if disease progression did not occur (the date of progression or death or censoring - date of randomization + 1). Subjects for whom neither death nor progression have been documented will be censored at the date of the last radiological assessment that the subject was progression-free. If a subject has no post-baseline radiological assessment, then the data will be censored at the date of randomization.

Subjects with two or more missing assessments prior to a visit with documented disease progression (or death) will be censored at the last assessment where the subject was documented to be progression free. Subjects who received new anti-cancer therapy or cancer-related surgery prior to progression or death will not be censored at the last assessment where the patient was documented as progression free prior to the new anti-cancer therapy or cancer-related surgery. Censoring rules are documented in section 15.2.

The following PFS analyses will be performed at 2-sided significance level $\alpha=0.05$ for exploratory purpose. The stratified LogRank test will be applied on the PFS time to test for differences between the 2 treatment groups. The Cox's proportional hazards model stratified by the stratification factors assessed at randomization (except institution) will provide the HR (including 95% CI). Summary of associated statistics for each treatment arm (median PFS time, 6-, 12-, 18-, 24-month PFS rate estimates and estimates for every 6 months thereafter as applicable) will be displayed with 95% CI computed using the same methods as for OS, and the Kaplan-Meier curve for PFS will be presented.

Progression-free survival Kaplan-Meier estimates will be calculated and unstratified Cox's proportional hazards model will be fitted for each subgroup defined in Section 11.5 in the ITT population only. Forest Plot will be displayed with a subgroup by treatment interaction test.

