15.2. Censoring Rules for PFS

Situation	Date of Progression or Censoring	Situation/Outcome
No baseline assessments and alive after 2 scheduled assessments	Randomization	Censored
Death within the first two scheduled assessments without any adequate assessment	Date of death	Event
Death between adequate assessments	Date of death	Event
No progression	Date of last adequate assessment with evidence of no progression	Censored
Study discontinuation for reasons other than disease progression or death	Date of last adequate assessment with evidence of no progression	Censored
New anti-cancer therapy or cancer-related surgery prior to progression or death	Date of last adequate assessment after start of new anti-cancer therapy or cancer-related surgery with evidence of progression prior	Event
	Date of last adequate assessment after start of new anti-cancer therapy or cancer-related surgery with evidence of no progression	Censored
Death or progression after an extended lost-to-follow-up time (two or more missed scheduled assessments)	Date of last adequate assessment with evidence of no progression	Censored

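### Protocol 5.3 lets tumour assessment end when a new regimen starts, whereas the follow-up schedule and the PFS definition need it to continue to progression

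*Protocol*

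**What the plan says.** Protocol 5.3 covers patients who discontinue treatment for a reason other than progression. For them, "whenever possible, tumor assessment will continue as per protocol until disease progression, or start of a new treatment regimen".

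Other sections set a different end point. Protocol 6.3.2.1, on follow-up of patients who have not progressed, has standard-of-care MRI results collected, "or done as per the study schedule of every 8 weeks (continuing on initial schedule) until disease progression". Footnote p of table 6.4 says the same. Protocol 7.1.1.3 states: "Follow-up assessments will be performed every 8 weeks (or earlier if clinically indicated) until disease progression". None of these stops at new therapy, and 6.3.2.1 lists subsequent regimens among the items recorded for the same unprogressed patients. The protocol summary first promises MRI every 8 weeks until progression and then adds: "Once patients stop study treatment, they will be followed as per institution's standard".

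On the endpoint, Protocol 7.1.3 says: "Patients who received new anti-cancer therapy or cancer-related surgery prior to progression or death will not be censored at the last assessment". SAP 11.3.1 repeats the rule. SAP 15.2 has two rows for these patients, one for an event and one for censoring, and both rest on an assessment made after the switch. The censoring row uses "Date of last adequate assessment after start of new anti-cancer therapy or cancer-related surgery with evidence of no progression". Separately, Protocol 7.1.3 provides: "Patients with two or more missing response assessments prior to a visit with documented disease progression (or death) will be censored". That censoring falls at the last progression-free visit, and SAP 15.2 carries the same rule for progression or death after two or more missed scheduled assessments.

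**The concern.** The PFS rule for switchers works only if assessment continues after the switch, and 5.3 allows it to stop there. A site can comply with 5.3 and have no scan after new therapy begins, while another follows 6.3.2.1 and collects every scan. No text says which section prevails.

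At stake is whether PFS is measured as defined. If switching before documented progression is related to the risk of progression, censoring at the last scan before the switch is informative. If switching also differs between arms, the PFS hazard ratio is biased. The trial is open label. SAP 3 notes that marizomib will be discontinued by physician or patient decision after the IDMC review, which may enlarge the off-treatment, unprogressed group in one arm before the long-term follow-up analysis. SAP 5.2.2 names PFS as the key secondary endpoint.

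**Working it through.** The plan states no figure on this point, so there is nothing to reproduce. The check sets the passages side by side and follows one type of patient through them.

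**Who is affected.** Protocol 5.6.3 makes systemic anti-cancer therapy or craniotomy before progression a cause for leaving study treatment. Such a patient has discontinued for a reason other than progression and so falls under the 5.3 sentence.

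**When assessment ends for this patient**

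| Source | End of tumour assessment |
|---|---|
| Protocol 5.3 | Progression or new regimen |
| Protocol 6.3.2.1; table 6.4, footnote p | Progression (standard-of-care results or 8-weekly scans) |
| Protocol 7.1.1.3 | Progression (8-weekly) |
| Protocol summary | Progression, then institutional standard once off treatment |

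**Outcome under SAP 15.2 if the site follows 5.3 and no assessment exists after the switch**

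1. Neither switch row applies, because both need an assessment after the switch.
2. Alive with no recorded progression: the general no-progression row applies, and the patient is censored at the last scan, which precedes the switch.
3. Progression or death after two or more missed scheduled assessments: censored at that same scan, provided that scans not required under 5.3 count as missed. The SAP does not say whether they do.
4. Death before two assessments have been missed: still a PFS event.
5. Progression recorded on clinical grounds: Protocol 7.1.1.4 accepts definite clinical deterioration, or failure to return because of death or deteriorating condition, so an event can be recorded without a scan (subject to step 3 if it comes late).

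**How often step 4 would keep the event.** With 8-weekly scans, two missed scans span about 16 weeks from the last scan. Depending on when the switch falls between scans, 8 to 16 weeks of that window remain. Median survival from the switch is not in the documents; 6 to 16 months is assumed, with exponential survival. Using the SAP's 30.4375 days per month, 8 weeks is 56/30.4375 = 1.84 months and 16 weeks is 112/30.4375 = 3.68 months. Then

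P(death inside the window) = 1 − 2^(−t/median)

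| Assumed median from switch | 8 weeks left | 16 weeks left |
|---|---|---|
| 6 months | 19.1% | 34.6% |
| 9 months | 13.2% | 24.7% |
| 12 months | 10.1% | 19.1% |
| 16 months | 7.7% | 14.7% |

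So even where 5.3 is applied literally, roughly 8% to 35% of switchers would keep a death event under these assumptions. Censoring before the switch would be common at such sites but not universal. Where 6.3.2.1 and 7.1.1.3 are followed, the schedule does not cause it.

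**The case against.** The strongest reply is that 5.3 is a treatment-duration section and forbids no later scan, while every section that sets the assessment schedule runs to progression. Protocol 5.4 has the progression date collected whenever feasible, and patients who themselves choose to stop treatment must be followed for disease assessments. The summary's sentence on institutional standard directly follows one promising MRI until progression. There is also a tension in the censoring chain: if 5.3 governs, it is unclear that a scheduled scan was missed, and if 7.1.1.3 governs, scans continue.

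Much of this stands. A reader might infer that the plan as a whole censors patients at the switch; the documents do not support that. It is a risk at sites that apply 5.3 alone. The reply does not remove the contradiction, because no text ranks the sections and SAP 15.2 has no row for a switcher with no later assessment.

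A reader might also infer a PFS hazard ratio biased in favour of marizomib. An illustrative simulation with no true effect, exponential PFS with an assumed median of 30 or 39 weeks, and every switcher censored before progression gives a hazard ratio of about 0.95 to 0.98 if 5% of control and 10% of marizomib patients switch. Reversing the shares gives about 1.02 to 1.05 (1/0.98 and 1/0.95), and equal shares give about 1. The shares and medians are assumptions, and taking every switcher's event as lost overstates the effect. Nor do the documents show that marizomib toxicity leads to a new regimen: Protocol 5.3 has the other drug continue alone when one is stopped for a reason other than progression.

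**Conclusion.** The contradiction is real. Protocol 5.3 does not fit 6.3.2.1, footnote p of table 6.4, 7.1.1.3, the PFS definition in Protocol 7.1.3 and SAP 11.3.1, or the switch rows of SAP 15.2. Where 5.3 is applied literally, some patients who switch before progression can be censored at their last scan before the switch, contrary to the stated rule.

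The number affected and the size and direction of any bias are unknown, since they depend on switching shares by arm and on which section sites followed. The 8% to 35% range for retained deaths rests on assumed survival after the switch. PFS is tested at an exploratory two-sided 5% level without multiplicity adjustment, and OS is unaffected. The point should be corrected but does not threaten the primary conclusion.

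**What to change.** - **Protocol 5.3:** delete the alternative stop at a new regimen, so that the sentence matches 6.3.2.1 and 7.1.1.3. Keep the choice in 6.3.2.1 between standard-of-care results and 8-weekly scans.
- **Protocol summary:** align the institutional-standard sentence with the MRI-until-progression sentence before it.
- **SAP 15.2:** add a row for a switcher with no assessment after the switch, and state whether scans not required under 5.3 count as missed.
- **Follow-up analysis:** retrieve the standard-of-care MRI results after the switch that 6.3.2.1 already provides for. Report by arm the number of patients who switched before progression and the number of these with no later assessment.

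Recruitment is closed and the primary analysis uses the 28 April 2020 cut-off, so the text change cannot create scans that were not done. Retrieval and reporting remain possible for the descriptive follow-up analysis. The cost is a short wording correction, a SAP clarification and extra data entry for a minority of patients.

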## 5.4 Withdrawal criteria

The principal investigator should discontinue study treatment for a patient in the event of:

- Progressive disease
- Unacceptable overall toxicity for all drugs.
- Protocol violation
- Loss to follow-up

- Patient significant non-compliance
- Pregnancy
- Physician/Patient decision
- Death

An end of treatment visit should be performed, and follow-up for survival, subsequent therapy and date of progressive disease (PD) collected, whenever feasible.

**Patients have the right to withdraw from the study at any time for any reason.**

In the case that the patient decides to prematurely discontinue study treatment, the patient must be followed for disease assessments and survival follow-up, unless the patient decides to withdraw consent for the collection of these data. In the case that the patient withdraws consent, the patient must be asked if can still be contacted for survival follow-up only. The outcome of these discussions should be documented in both the medical records and in the eCRF.

## 5.5 Dose and schedule modifications

Treatment (MRZ +TMZ) may be administered -1 / +3 days of a scheduled dose for reasons other than toxicity.

### 5.5.1 MRZ

Acceptable MRZ dose reductions are as follows:

| Dose Level     | Weekly dose            | Concomitant Treatment Schedule | Adjuvant Treatment Schedule     |
|----------------|------------------------|--------------------------------|---------------------------------|
| Starting dose  | 0.8 mg/m   | Days 1, 8, 15, 29, 36          | Days 1, 8 and 15 (28-day cycle) |
| Dose level -1  | 0.7 mg/m   | Days 1, 8, 15, 29, 36          | Days 1, 8 and 15 (28-day cycle) |
| Dose level - 2 | 0.55 mg/m  | Days 1, 8, 15, 29, 36          | Days 1, 8 and 15 (28-day cycle) |
| Dose level - 3 | 0.4 mg/m   | Days 1, 8, 15, 29, 36          | Days 1, 8 and 15 (28-day cycle) |

The minimum permitted dose level for MRZ is 0.4 mg/m^2. If toxicity recurs at the minimum permitted dose of MRZ, MRZ treatment should be discontinued. Dose re-escalation is not permitted for MRZ.

Minimum re-treatment criterion prior to the beginning of each new cycle in the adjuvant treatment: creatinine  $\leq$  1.5 x ULN, Hgb  $\geq$  8 g/dL, platelets  $\geq$  75 x 10^9/L.

**During adjuvant phase: Marizomib treatment may be held (skipped) a maximum of 3 consecutive doses for related toxicity.**

**If the 3 consecutive skipped doses are in the same cycle, and the subject is able/unable to resume marizomib on the scheduled Day 1 of the subsequent cycle, the Medical Monitor should be contacted to discuss continuation or permanent withdrawal of marizomib.**

**If the 3 consecutive skipped dose are in 2 consecutive cycles, and the patient is able/not able to resume treatment at the next planned visit, the Medical Monitor should be contacted to discuss continuation of marizomib or permanent withdrawal.**

**MRZ delays: -1day to +3 days: MRZ can be administered 1 day before and up to 3 days after the planned administration. The next dose will be administered at the next initially planned visit.**

Detailed instructions for MRZ dose modifications and actions are provided in the Table below:

| Marizomib-Related Adverse Event   | Severity | Recommended action regarding MRZ administration   |
|---|----------|---|
| Central Nervous System   |          |   |
| Common CNS AEs include:

Hallucinations, ataxia, dizziness, gait disturbance, balance disorder, fall, dysarthria, confusion | Grade 2  | Consider other supportive treatment; generally no dose-reductions are recommended.

Dose-reduction is recommended if intolerable by patient due to interference with daily routine and/or if duration of event lasts longer than 3 days.  |
|   | Grade 3  | At the next scheduled MRZ dose administration, dose-reduce one dose level.

During concomitant treatment, if AE has not resolved to $\leq$ Grade 1 (or baseline) by the next scheduled dose of MRZ, skip MRZ and administer TMZ/RT without delay; consider dose reduction with the next scheduled dose.

During adjuvant treatment, if AE has not resolved to $\leq$ Grade 1 (or baseline) by Day 1 of next cycle, administer Day 1 TMZ and skip the Day 1 MRZ dose. Resume MRZ with the next scheduled dose at reduced level.

If AE has not resolved to $\leq$ Grade 1 (or baseline) by Day 1 of next cycle, administer Day 1 TMZ and skip the Day 1 MRZ dose. Resume MRZ with the next scheduled dose at reduced level.

If AE has not resolved to $\leq$ Grade 1 (or baseline) on Days 8 or 15, skip the MRZ dose and resume with the next scheduled dose at reduced level.

If AE has not resolved to $\leq$ Grade 1 (or baseline) during adjuvant MRZ post-completion of TMZ, delay and reduce the MRZ dose.

In addition, consider other supportive treatment. |
|   | Grade 4  | Stop MRZ until resolution to $\leq$ Grade 1 (or baseline).

Discuss with Medical Monitor.

If re-challenge is an option, reduce MRZ dose level (see MRZ dose reduction table) in agreement with Medical Monitor.  |

| Marizomib-Related Adverse Event | Severity     | Recommended action regarding MRZ administration   |
|---------------------------------|--------------|---|
| Gastrointestinal         |              |   |
| Nausea, Vomiting                | Grade 1 or 2 | 
Implement prophylactic anti-emetic regimen according to local guidelines.
 
Maintain current MRZ dose schedule without dose modification.
 
If (re)occurrence despite appropriate prophylaxis, dose-reduce one dose level (see MRZ dose reduction table) at the next scheduled MRZ dose administration.
  |
|                                 | Grade 3 or 4 | 
Implement prophylactic anti-emetic regimen according to local guidelines.
 
If (re)occurrence despite appropriate prophylaxis, dose-reduce one dose level (see MRZ dose reduction table) at the next scheduled MRZ dose administration.
 
In addition, consider other supportive treatment per local guidelines.
   |
| Other Adverse Events     |              |   |
|                                 | Grade 2      | 
Maintain current MRZ dose schedule without dose modification.
 
Consider dose-reduction if intolerable by patient due to interference with daily routine and/or not resolved to <math>\leq</math> Grade 1 (or baseline) at the next scheduled MRZ dose administration.
  |
|                                 | Grade 3      | 
At the next scheduled MRZ dose administration, dose-reduce one dose level (see MRZ dose reduction table).
 
During concomitant treatment, if AE has not resolved to <math>\leq</math> Grade 1 (or baseline) by the next scheduled dose of MRZ, skip MRZ and administer TMZ/RT without delay; consider dose reduction with the next scheduled dose.
 
During adjuvant treatment, if AE has not resolved to <math>\leq</math> Grade 1 (or baseline) by Day 1 of next cycle, administer Day 1 TMZ and skip the Day 1 MRZ dose. Resume MRZ with the next scheduled dose at reduced level.
 
If AE has not resolved to <math>\leq</math> Grade 1 (or baseline) by Day 1 of next cycle, administer Day 1 TMZ and skip the Day 1 MRZ dose. Resume MRZ with the next scheduled dose at reduced level.
 |

| Marizomib-Related Adverse Event   | Severity  | Recommended action regarding MRZ administration   |
|---|-----------|---|
|   |           | 
If AE has not resolved to <math>\leq</math> Grade 1 (or baseline) on Days 8 or 15, skip the MRZ dose and resume with the next scheduled dose at reduced level.
 
If AE has not resolved to <math>\leq</math> Grade 1 (or baseline) during adjuvant MRZ post-completion of TMZ, delay and reduce the MRZ dose.
 |
|   | Grade 4   | 
Stop MRZ until resolution to <math>\leq</math> Grade 1 (or baseline).
 
Discuss with Medical Monitor.
 
If re-challenge is an option, reduce MRZ dose level (see MRZ dose reduction table) in agreement with Medical Monitor.
  |
| When marizomib is administered as single agent (after completion of adjuvant temozolomide treatment) |           |   |
| Any MRZ-related AE  | Any grade | If patient is slow to recover from MRZ toxicity, a treatment delay can occur for each of the scheduled marizomib doses as needed.   |

